10.3 Subject Disposition

- **Enrolled Subjects:** Patients who sign the ICF.
- **Excluded Subjects:** Subjects who are enrolled but never undergo insertion of the study catheter. Excluded subjects will be subjected to safety event reporting between ICF signature and date of exclusion. Subjects who signed the ICF but are found to be ineligible prior to insertion of the catheter are also considered as excluded.
- **Discontinued Subjects:** Enrolled subjects who have the study catheter inserted but no assessments are performed with it. Discontinued subjects will remain in follow-up for 7 days for safety evaluation.
- **Lost to Follow-up Subjects:** Enrolled subjects of which contact is lost after most recent visit (despite 3 documented attempts to contact the subject).
- **Withdrawn / Early Termination Subjects:** Subjects who withdraw consent for study participation or are withdrawn by the investigator, are terminated from the study prior to completion of all follow-up visits.
- **Completed Subjects:** Enrolled subjects who have not been excluded, discontinued, withdrawn, terminated early, or lost-to-follow-up from the study prior to the final study visit.

11. Responsibilities

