14.2.2 Study Procedure

Subjects will arrive to the electrophysiology laboratory for their study procedure and will undergo preparation for the procedure per the hospital's standard protocol (discretion of investigator)

Overall Use of the Investigational Device

During study procedures, investigators will use the investigational catheter instead of the institution's standard ultrasound catheter choice (e.g. SOUNDSTAR™). Any use of a non-investigational ultrasound device will be considered a failure of the primary performance endpoint.

The use of the investigational NUVISION™ NAV Ultrasound Catheter is **mandatory** for:

- Thrombus detection and LA/LV imaging for volume measurement at the start of the procedure;
- During transeptal puncture;
- And as navigational ULS catheter throughout the procedure.

Imaging guidance for LA/LV volume measurements:

- Capture preferably the full chamber in one ULS volumetric segment, if needed several segments can be taken.
- For capturing of the LA:
 - Capture 4D ULS clip (full 90°x90°) of the LA (with PVs and LAA) taken from the RA.
 - Repeat the acquisition from 3-6 slightly different positions, where the LA volume is partial.
Note: Capture 4D ULS clip before transeptal and insertion of any other catheters to the LA, by using the default ULS settings, and without using the "zoom" function.
 - Place the investigational NUVISION™ NAV Ultrasound Catheter near the interatrial septum and make sure to capture the ENTIRE left atrium.
 - Confirm by seeing both anterior-posterior and Roof to Mitral valve planes.
 - Make sure to allow sufficient ULS depth by visualizing the distal LAA.
- For capturing of the LV:
 - The catheter can be positioned either in the RA near the inferior septum or in the right ventricle (RV) near the interventricular septum.
 - Make sure to allow sufficient ULS depth by visualizing the entire chamber from the Mitral valve to the distal apex.

Investigators should use the CARTO™ 3 system to **"bookmark"** instances of abnormal study catheter "imaging noises". This will allow for further analysis of the data.

Standard of Care Ablation Procedure

Treatment will be per institution's standard of care (SOC).

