20.3 Analysis Sets

Safety Analysis Set: The Safety Analysis Set will consist of all enrolled subjects who have undergone insertion of the NUVISION™ NAV Ultrasound catheter.

Per Protocol (PP) Analysis Set: The PP Analysis Set will include all enrolled subjects who met the study eligibility criteria and in whom assessments were performed with the NUVISION™ NAV Ultrasound catheter.

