20.4.6 Analysis for Primary Endpoints

Primary Performance Endpoint is defined as the completion of imaging required for the study procedure with the NUVISION™ NAV Ultrasound Catheter without resort to non-study ultrasound device(s).

The number of subjects who successfully completed the procedure without resort to a non-study ultrasound device will be summarized overall and per procedure type (atrial ablation/ventricular ablation) for the PP Analysis Set.

A listing of the primary performance endpoint will be provided.

Primary Safety Endpoint is defined as the occurrence of serious adverse events related to the Investigational catheter within 7 days of index procedure. An SAE will be counted as related to the investigational catheter if the relationship to a study catheter is anything other than 'Not Related'.

The number of subjects with SAEs related to the investigational catheter will be summarized in the Safety Analysis Set overall and per procedure type (atrial ablation/ventricular ablation) by System Organ Class and Preferred Term and level of relationship. All tables will present summaries both by subject and by event. If a subject has multiple occurrences of an event within a level of summarization, then for the by-subject summaries only a single occurrence will be counted at each level of summarization at the highest level of severity/relationship; for the by-event summary all events will be counted.

All investigational catheter related SAEs will be listed by System Organ Class and Preferred Term, severity, causality (defined as possible, probable or having a causal relationship to the device and/or procedure), anticipation and outcome.

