## 6 Analysis Sets

Safety Analysis Set: The Safety Analysis Set will consist of all enrolled subjects who have undergone insertion of the NUVISION™ NAV Ultrasound catheter.

**Per Protocol (PP) Analysis Set**: The PP Analysis Set will include all enrolled subjects who met the study eligibility criteria and in whom assessments were performed with the NUVISION™ NAV Ultrasound catheter.

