## 8.5 Analysis of Primary Endpoint(s)

Primary Safety Endpoint is defined as the occurrence of serious adverse events related to the Investigational catheter within 7 days of index procedure. An SAE will be counted as related to the investigational catheter if the relationship to a study catheter is anything other than 'Not Related'.

The number of subjects with SAEs related to the investigational catheter will be summarized in the Safety Analysis Set overall and per procedure type (atrial ablation/ventricular ablation) by System Organ Class and Preferred Term and level of relationship. All tables will present summaries both by subject and by event. If a subject has multiple occurrences of an event within a level of summarization, then for the by-subject summaries only a single occurrence will be counted at each level of summarization at the highest level of severity/relationship; for the by-event summary all events will be counted.

All investigational catheter related SAEs will be listed by System Organ Class and Preferred Term, severity, causality (defined as possible, probable or having a causal relationship to the device and/or procedure), anticipation and outcome.

Primary Performance Endpoint is defined as the completion of imaging required for the study procedure with the NUVISION™ NAV Ultrasound Catheter without resort to non-study ultrasound device(s).

The number of subjects who successfully completed the procedure without resort to a non-study ultrasound device will be summarized overall and per procedure type (atrial ablation/ventricular ablation) for the PP Analysis Set.

A listing of the primary performance endpoint will be provided.

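### Primary performance is reported only in the Per Protocol set, which drops a Discontinued subject switched to another ultrasound device instead of counting a failure

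*SAP*

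**What the plan says.** **Endpoint and failure rule.** The endpoint is completion of the imaging needed for the procedure with the study catheter and no other ultrasound device (Protocol 8.2.1, SAP 8.4.1). Protocol 14.2.2 adds: "Any use of a non-investigational ultrasound device will be considered a failure of the primary performance endpoint". The synopsis repeats this rule.

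**Summary.** Protocol 20.4.6 states: "The number of subjects who successfully completed the procedure without resort to a non-study ultrasound device will be summarized overall", and then by procedure type, in the Per Protocol (PP) set. SAP 8.5 has the same text, ending "overall and per procedure type (atrial ablation/ventricular ablation) for the PP Analysis Set". The synopsis asks for a proportion as well as a count and names no set.

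**Sets.** SAP 6 says "The PP Analysis Set will include all enrolled subjects who met the study eligibility criteria and in whom assessments were performed with the" study catheter. Protocol 20.3 has the same condition: "in whom assessments were performed with the NUVISION™ NAV Ultrasound catheter". For safety, SAP 6 says "The Safety Analysis Set will consist of all enrolled subjects who have undergone insertion of the" study catheter.

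**Discontinued subjects.** Protocol 10.3 defines them as "Enrolled subjects who have the study catheter inserted but no assessments are performed with it", and says "Discontinued subjects will remain in follow-up for 7 days for safety evaluation".

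**The concern.** Entry to the PP set depends partly on the outcome being measured. A catheter that is inserted, yields no assessment and is replaced by another ultrasound device is the most complete performance failure the protocol describes, and it is the kind that the PP condition removes. A partial failure stays in the set and counts. Leaving out a failure can only raise a success rate that is below 100%, or keep it at 100%.

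At stake is the descriptive accuracy of the primary performance result in a first-in-human study (Protocol 6.3). The set should be fixed before results are seen, because a later choice between two denominators would be open to challenge.

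**Working it through.** The plan has no calculated figure to reproduce. SAP 7 bases the 30 subjects on previous experience, with no target rate or precision.

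**Step 1: who is in which set**

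| Eligible subject, catheter inserted | Safety set | PP set | Status under 14.2.2 | In the reported rate? |
|---|---|---|---|---|
| All required imaging with study catheter, no other device | yes | yes | success | yes |
| Some assessments, then switched | yes | yes | failure | yes, as a failure |
| No assessments, switched (Discontinued) | yes | no | failure | **no** |
| No assessments, not switched (Discontinued) | yes | no | not covered by the device-use rule | no |

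The third row is the gap. Protocol 10.2 describes replacement only before insertion, so such a subject shrinks the denominator.

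**Step 2: size**

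Let N be eligible inserted subjects, k those Discontinued and switched, and f other failures, which stay in PP.

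- PP rate = (N − k − f)/(N − k)
- All-inserted rate = (N − k − f)/N

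The number of successes is the same in both. Only the failures and the denominator differ. N = 30 comes from SAP 7, on the assumption that all 30 have the catheter inserted and are eligible. The values of k and f are assumptions. Intervals are exact (Clopper-Pearson) two-sided 95%. The level is from SAP 5; the method is assumed here.

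| k | f | PP | All inserted | Gap, points |
|---|---|---|---|---|
| 0 | 0 | 30/30 = 100% (88.4 to 100) | 30/30 = 100% (88.4 to 100) | 0 |
| 1 | 0 | 29/29 = 100% (88.1 to 100) | 29/30 = 96.7% (82.8 to 99.9) | 3.3 |
| 2 | 0 | 28/28 = 100% (87.7 to 100) | 28/30 = 93.3% (77.9 to 99.2) | 6.7 |
| 3 | 0 | 27/27 = 100% (87.2 to 100) | 27/30 = 90.0% (73.5 to 97.9) | 10.0 |
| 1 | 1 | 28/29 = 96.6% (82.2 to 99.9) | 28/30 = 93.3% (77.9 to 99.2) | 3.2 |

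With f = 0, PP shows 100% whatever the value of k.

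**Step 3: by procedure type**

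For an assumed stratum with k = 1 and f = 0, PP is 100% in each case. The all-inserted rate is 14/15 = 93.3%, 9/10 = 90.0% or 4/5 = 80.0% for 15, 10 or 5 subjects.

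**Step 4: chance that it arises**

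If each of 30 subjects had probability p of being Discontinued and switched, the chance of at least one is 1 − (1 − p)^30. This gives 26%, 45% and 79% for assumed p of 1%, 2% and 5%. The documents give no value of p.

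**The case against.** **The group is narrow.** This stands. Protocol 14.2.2 places thrombus detection and chamber imaging at the start of the procedure, so most inserted subjects will have some assessment and enter PP. One might infer that PP removes every subject switched to another device. It does not: a partly imaged and then switched eligible subject stays in and counts as a failure.

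**The subjects are visible elsewhere.** This largely stands, and a reader who infers that the failures are hidden would be wrong. SAP 8.2 and Protocol 20.4.3 summarise and list disposition by the 10.3 categories for all subjects, and give the numbers in each set. SAP 8.6 and Protocol 20.4.7 list device deficiencies with no PP restriction, so a device-caused imaging failure should appear there. The endpoint listing in SAP 8.5 names no set. From these a reader could bound the all-inserted rate. It remains unclear whether the summary of reasons for premature discontinuation covers the 10.3 Discontinued category, whose subjects stay in follow-up. None of these outputs changes the rate.

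**The study is descriptive.** This stands. SAP 5 excludes hypothesis testing and SAP 7 excludes effectiveness claims, so no decision rule changes.

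**Counting every Discontinued subject as a failure goes beyond the protocol's rule.** This stands in part. Without use of another device, 14.2.2 does not name the subject a failure. Counting such a subject as not successful follows from the completion wording of the endpoint, but includes procedures stopped for reasons unrelated to the device. That is a choice to be stated openly, and those cases are not part of the size shown above.

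**PP also drops ineligible inserted subjects.** True, but this is a separate exclusion that can move the rate either way. It should not be read as further evidence of inflation.

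**Conclusion.** The point holds in this limited form. Followed as written, the plan leaves a defined failure out of the primary performance rate whenever a Discontinued subject is switched to a non-study ultrasound device during the procedure. With N = 30 and no other failure, each such subject costs about 3.3 percentage points that the PP rate does not show. The cost is larger within a small procedure-type stratum. With no such subject, this exclusion has no effect.

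The sizes rest on assumed counts and on all 30 subjects being inserted and eligible. The conclusion about the sets rests only on the documents' own definitions. It does not mean that the reported rate will be wrong, only that it would be if such a case occurred. It is worth correcting because the remedy is simple and the analysis set already exists.

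**What to change.** In SAP 8.5 and Protocol 20.4.6:

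- Report the performance endpoint in the Safety Analysis Set, with all inserted subjects as the denominator, and keep PP as a supportive line.
- Count as not successful any inserted subject who did not complete the required imaging with the study catheter, or in whom a non-study ultrasound device was used **during the study procedure**. The time limit is needed: Protocol 14.2.1 itself provides for a baseline transthoracic echo, and imaging outside the procedure should not count.
- State that these subjects are observed non-successes, not missing. SAP 8.1 and Protocol 20.4.1 base percentages on subjects without missing data, so a blank endpoint field could remove them again. This is a precaution; nothing in the plan says the field would be blank.
- List the cause for each Discontinued subject, so that procedures stopped for reasons unrelated to the device can be seen.
- Name the set for the endpoint listing and in SAP 8.9, which names none for the arrhythmia subgroups. Note that the Safety set also brings back inserted subjects later found ineligible.

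**Cost.** The SAP needs a revision of wording. The protocol needs a written amendment by the approval route in its section 17. Non-study ultrasound use and the cause of non-assessment must be recorded for every inserted subject. The reported rate may be slightly lower, also when the cause was not the device; the PP line and the cause listing make that visible.

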## 8.6 Analysis of Secondary Endpoint(s)

Secondary Safety Endpoints will be analyzed using the Safety Analysis Set:

 All Serious Adverse Events, excluding investigational catheter related SAE, during the 7-day follow-up period.

 All non-serious Adverse Events related to the investigational catheter during the 7day follow-up period

The number of subjects experiencing serious adverse events excluding investigational catheter related SAE and the number of serious adverse events excluding investigational catheter related SAE will be summarized in the Safety Analysis Set overall and per procedure type (atrial ablation/ventricular ablation) using categorical summaries similar to the primary safety endpoint.

The number of subjects experiencing non-serious adverse events related to the investigational catheter and the number of non-serious adverse events related to the investigational catheter will be summarized in the Safety Analysis Set overall and per

procedure type (atrial ablation/ventricular ablation) using categorical summaries similar to the primary safety endpoint.

All SAEs excluding investigational catheter related SAE and all non-serious AEs related to investigational catheter will be listed by System Organ Class and Preferred Term, severity, causality (defined as possible, probable or having a causal relationship to the device and/or procedure), anticipation and outcome.

A listing of device deficiencies including the category and timing of the device deficiency will also be provided. Each deficiency will indicate whether it results in an adverse event.

Physician feedback on deployment, maneuverability, navigational features and imaging quality acquired with the investigational catheter will be analyzed using the PP Analysis Set. A post-procedure survey will be administered. Each question/subquestion will be answered by the physician using a Likert scale of 1 to 7 (1=poor and 7=excellent) and will be summarized. The summary results of each question will be presented overall and per procedure type (atrial ablation/ventricular ablation) using continuous summaries. A by subject listing including all feedback results will be provided.

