14.2.4 Data Collection during Study Ablation Procedure

Procedural parameters collected during the procedure include but are not limited to:

- Anatomical structures assessed
- Imaging for Left Atrium (LA) and Left Ventricle (LV) volume measurements
- Total fluoroscopy time
- Total procedure duration.

Following each procedure, physician feedback on the investigational catheter and associated software used will be collected, using a 7-point Likert-scale survey; it will include feedback on deployment, maneuverability, navigational features and imaging quality acquired. The survey will be entered into the eCRF for analysis.

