20.4.7 Analyses of Secondary Endpoints

Secondary Safety Endpoints will be analyzed using the Safety Analysis Set:

- All Serious Adverse Events, excluding investigational catheter related SAE, during the 7-day follow-up period.
- All non-serious Adverse Events related to the investigational catheter during the 7-day follow-up period

The number of subjects experiencing serious adverse events excluding investigational catheter related SAE and the number of serious adverse events excluding investigational catheter related SAE will be summarized in the Safety Analysis Set overall and per procedure type (atrial ablation/ventricular ablation) using categorical summaries similar to the primary safety endpoint.

The number of subjects experiencing non-serious adverse events related to the investigational catheter and the number of non-serious adverse events related to the investigational catheter will be summarized in the Safety Analysis Set overall and per procedure type (atrial ablation/ventricular ablation) using categorical summaries similar to the primary safety endpoint.

All SAEs excluding investigational catheter related SAE and all non-serious AEs related to investigational catheter will be listed by System Organ Class and Preferred Term, severity, causality (defined as possible, probable or having a causal relationship to the device and/or procedure), anticipation and outcome.

A listing of device deficiencies including the category and timing of the device deficiency will also be provided. Each deficiency will indicate whether it results in an adverse event.

Physician feedback on deployment, maneuverability, navigational features and imaging quality acquired with the investigational catheter will be analyzed using the PP Analysis Set. A post-procedure survey will be administered. Each question/sub-question will be answered by the physician using a Likert scale of 1 to 7 (1=poor and 7=excellent) and will be summarized. The summary results of each question will be presented overall and per procedure type (atrial ablation/ventricular ablation) using continuous summaries. A by subject listing including all feedback results will be provided.

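### Both documents summarise the physician survey in the Per Protocol set, so deployment and maneuverability ratings from procedures where the catheter was inserted but not used are left out of the summary statistics

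*SAP*

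**What the plan says.** Protocol 14.2.4 sets the collection rule: "Following each procedure, physician feedback on the investigational catheter and associated software used will be collected, using a 7-point Likert-scale survey". On content, "it will include feedback on deployment, maneuverability, navigational features and imaging quality acquired". No exception is made for a procedure in which the catheter was inserted and then not used. The endpoint definition (Protocol 8.2.2, SAP 8.4.2) is likewise not limited to procedures that produced assessments.

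For analysis, SAP 8.6 states: "Physician feedback on deployment, maneuverability, navigational features and imaging quality acquired with the investigational catheter will be analyzed using the PP Analysis Set". Protocol 20.4.7 agrees: "imaging quality acquired with the investigational catheter will be analyzed using the PP Analysis Set". Each question is scored 1 to 7 and reported with continuous summaries, overall and by procedure type (atrial or ventricular). A by-subject listing of all feedback is also promised, without naming its population.

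SAP 6 and Protocol 20.3 define PP as "all enrolled subjects who met the study eligibility criteria and in whom assessments were performed" with the study catheter. The Safety Analysis Set is every enrolled subject in whom the catheter was inserted. Protocol 10.3 names the group that lies between the two sets, Discontinued subjects: "Enrolled subjects who have the study catheter inserted but no assessments are performed with it".

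**The concern.** Membership of the PP set depends partly on what two of the survey items measure. A catheter that could not be deployed or steered well enough to image anything would leave its subject outside PP. The deployment and maneuverability ratings for that procedure would then leave the summary because of the handling they describe. The eligibility condition also removes ratings, for a reason that has nothing to do with handling.

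The secondary objective is to characterise physician feedback on these features. The study is first in human, and its stated purpose includes feasibility for further product development (Protocol 6.3 and 7.2). Poor handling experiences are among the most useful for that aim. Navigation and imaging quality are different: without an assessment there is little to rate, so restricting those items to subjects with assessments is reasonable.

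**Working it through.** **No figure to reproduce.** The sample size of 30 rests on previous experience (SAP 7, Protocol 20.2). There is no hypothesis test, precision target or success threshold for the survey.

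**Set membership, from the definitions**

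| Situation | Survey due (Protocol 14.2.4) | Safety set | PP set |
|---|---|---|---|
| Eligible, some assessment performed, even if another device was then used | Yes | In | In |
| Inserted, no assessment performed (Discontinued) | Yes, no exception stated | In | Out |
| Found ineligible after insertion | Yes, no exception stated | In | Out |

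Protocol 10.2 provides for replacement only before insertion, so subjects in the last two rows are not replaced.

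**Illustration of size.** The documents give neither an expected number of such subjects nor expected ratings, so everything here is assumed. Take 30 insertions, k of them outside PP and rated r, and a PP mean of m.

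Safety-set mean = ((30 − k) × m + k × r) / 30

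Overstatement by PP = k × (m − r) / 30

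With m = 6, the PP summary reports 6.00 whatever k is. The Safety-set means would be:

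| k | r = 1 | r = 2 | r = 3 |
|---|---|---|---|
| 0 | 6.00 | 6.00 | 6.00 |
| 1 | 5.83 | 5.87 | 5.90 |
| 2 | 5.67 | 5.73 | 5.80 |
| 3 | 5.50 | 5.60 | 5.70 |

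Per excluded rating, the shift is (6 − 3)/30 = 0.10 to (6 − 1)/30 = 0.17.

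Letting m run from 5.0 to 6.5 and r from 1 to 3, the overstatement is 0.07 to 0.18 (k = 1), 0.13 to 0.37 (k = 2) and 0.20 to 0.55 (k = 3).

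**Other statistics.** With 28 ratings of 6 and two of 1, the median stays at 6 and the minimum falls from 6 to 1.

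**By procedure type.** The shift is larger because n is smaller. With an assumed 10 ventricular cases, nine rated 6 and one rated 1, the mean is (9 × 6 + 1)/10 = 5.5.

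**How likely is at least one Discontinued subject?** The chance is 1 − (1 − p)^30, where p is the assumed per-subject probability of insertion without assessment.

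| p | Chance of at least one in 30 |
|---|---|
| 1% | 26% |
| 2% | 45% |
| 5% | 79% |
| 10% | 96% |

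**The case against.** Several stronger readings are tempting, and the documents do not support them.

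- *The SAP departs from the protocol.* It does not. Protocol 20.4.7 names the same set. Collecting more widely than one summarises is ordinary, so this is a choice of analysis set.
- *The excluded ratings vanish from the report.* This is not established. The by-subject listing is to include all feedback results and is not limited to PP. In a study of 30, a reader could see individual low scores there. Only the loss from the summary statistics is certain.
- *The planned minimum can never show bad handling.* That goes too far. PP requires that assessments were performed, not that imaging was completed. A catheter that handled badly, gave some assessment and was then replaced by another device stays in PP with its low scores.
- *Nothing else would reveal an unusable catheter.* Device deficiencies include inadequate usability (Protocol 15.1.5), and their listing in SAP 8.6 carries no PP restriction. Disposition tables report the Discontinued category. These sources hold no ratings, but they would show the event.
- *The bias is certain.* Protocol 10.3 gives no cause for discontinuation. Some procedures may stop for reasons unrelated to handling, and their ratings need not be low.

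It can also be said that Protocol 10.3 mentions only safety follow-up for Discontinued subjects, and that the survey form is not in the documents. Whether a physician would complete every item after an unused insertion therefore cannot be checked. Finally, the study is descriptive and makes no effectiveness claims, so no stated conclusion turns on a shift of this size.

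All of this stands and limits the reach of the point. It does not remove the fact that two handling items are summarised only where the catheter was used for at least one assessment.

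**Conclusion.** The point holds as a minor one. That the ratings leave the summary statistics follows directly from the definitions. That this biases the deployment and maneuverability scores upward is plausible, and depends on the catheter having gone unused because of poor handling. The size is unknown: about 0.10 to 0.17 points on the mean per excluded rating, assuming 30 insertions, a PP mean of 6 and excluded ratings of 1 to 3. The minimum could fall and the median may not move. If no subject is Discontinued or found ineligible after insertion, the PP and Safety results coincide.

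**What to change.** Make the same change in SAP 8.6 and Protocol 20.4.7:

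1. Summarise the deployment and maneuverability items in the Safety Analysis Set.
2. Keep the navigation and imaging-quality items for subjects in whom assessments were performed with the study catheter.
3. Show n for each item, so that the differing denominators are visible.
4. State that the by-subject listing covers all collected surveys, with Discontinued subjects flagged.

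This uses a set that is already defined and surveys that are already due, so it needs no new data collection. The cost is a few sentences in each document, possibly slightly less favourable scores, and denominators that differ between items. Settling it before results are known avoids a later choice made in view of the data.
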